4.5 Criteria for dosing

Doses are administered on day 1, 15, 29, 43, 57, 85, 113, and 141 (+/-3 days) if the patient is without ongoing Grade 3 non-hematologic or Grade 4 hematologic toxicities attributable to UC-961.

4.6 Dose Modifications and Dosing Delays

Each patient will be assessed for the development of toxicity according to the NCI Common Toxicity Criteria for Adverse Events (CTCAE), version 4.03 for non-hematologic toxicity or modified iwCLL criteria (section 7.1.2) for hematologic toxicity. Patients experiencing a DLT as defined in section 4.2 will be discontinued from study treatment. Otherwise, dose adjustments should be made according to the system showing the greatest degree of toxicity, as per 4.6.1, unless the adverse event is definitely unrelated to the study drug. Dose levels are listed in section 1.4.

- 2. UC-961 infusions can be delayed for a maximum of 28 days; if not restarted in that timespan, study treatment will be permanently discontinued.

- 3. If dose is decreased for Grade 3 or 4 toxicity, dose re-escalation is not planned.
- 4. For invasive procedures, not including biopsies or venous catheter placement: withhold study treatment for 1 week prior to procedure, and at least 1 week following surgery until satisfactory wound healing has been achieved.

4.6.2 Modifications for Infusion Reactions

Patients will be monitored for the presence of infusion-related reactions. Treatment for infusion-related reactions will be managed according to the following guidelines:

Infusion Reaction	Occurrence	Management Guidelines
Grade ≤ 2	any	Institute supportive measures.
		When resolved, resume study treatment at same dose level. Infusion rate adjustment per 4.4.
Grade 3	1st	Institute supportive measures.
		When resolved, resume study treatment at the same dose level. Infusion rate adjustment per 4.4. Premedications listed in protocol are mandatory for rechallenge.
	2nd	Institute supportive measures.
		Permanently discontinue study treatment.
Grade 4	any	Institute institutional procedures for adult medication reaction/anaphylactic response.
		Permanently discontinue study treatment.

4.7 Permitted concomitant therapy

Supportive Care

Appropriate antibiotics, anti-emetics, fluids, electrolytes and general supportive care are to be used as necessary.

Blood Products and Growth Factors

Blood products or myeloid growth factors can be administered for grade 4 toxicities (DLT), per investigator discretion for patient safety. The Principal Investigator ([name], MD PhD or [name], MD) should be called before growth factors are initiated. Erythropoietin or thrombopoietin mimetics are not to be used, unless continuation of a therapy that started ≥ 1 day prior to Cycle 1, Day 1.

4.8 Prohibited concomitant therapy

Concurrent Anticancer Therapy

Concurrent cancer therapy, including chemotherapy, radiation therapy, immunotherapy, or biologic therapy may NOT be administered to patients receiving study drug. Corticosteroids administration, even if for treatment of conditions other than CLL, at doses greater than

prednisone 20 mg daily (or equivalent dose of other steroids) are prohibited for greater than 14 days. If these treatments are administered the patient will be removed from study.

Investigational Agents

No other investigational agents may be given while the patient is on study.

4.9 **Duration of Therapy**

The investigational agent UC-961 will be administered until:

- a) Clinical or radiographic progressive disease.
- b) Unacceptable toxicities.
- c) Refusal of further protocol therapy by patient.
- d) Non-compliance that in the opinion of the investigator does not allow for ongoing participation.
- e) Completion of therapy.
- f) Physician determines it is in the patient's best interest to discontinue study agent.

Clinical Study Stopping Rules: Enrollment will be held pending review and approval by the UC San Diego Moores Cancer Center Data Safety Monitoring Board (DSMB) in the event of either of the following:

- Death. or
- 2 or more non-hematologic Grade 4 events at least possibly attributable to the study drug.

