DURATION OF INVESTIGATIONAL AGENT ADMINISTRATION AND STUDY PARTICIPATION

Duration of UC-961 administration is until disease progression, treatment intolerance, or lack of clinical benefit. Patients may remain on the clinical trial protocol until one of the following:

- Clinical or radiographic progressive disease (See Section 12).
- Adverse Events requiring removal from study (See Section 13).
- Refusal of further protocol therapy by patient/parent/guardian
- Non-compliance that in the opinion of the investigator does not allow for ongoing participation.
- Physician determines it is in the patient's best interest to discontinue participation in the clinical trial.
- Completion of all clinical trial procedures.

	Participation in the study and long-term follow-up will continue until one of the following:
	Death.
	Loss to follow-up.
	Withdrawal of consent for any further data submission.
	Progression requiring initiation of subsequent therapy.
	UC-961 is administered by intravenous infusion on day 1, 15, 29, 43, 57, 85, 113, and 141, after which responses will be assessed.
STUDY DRUG ADMINISTRATION	Patients with an objective response (meeting working group criteria for partial response or complete response) will continue at the same dose and schema. Patients with stable disease or progressive disease are eligible to increase the dose of UC-961 for another 6-month course.
CRITERIA TO EVALUATE SAFETY	Safety will be determined by Principal Investigator, and will be assessed according to the NCI Common Terminology Criteria for Adverse Events version 4.03 (NCI CTCAE v4.03) for non-hematologic toxicity and modified iwCLL criteria for hematologic toxicity.
CRITERIA TO EVALUATE EFFICACY	Overall response rate is the percentage of patients meeting criteria for partial response, nodular partial response, or complete response based on iwCLL criteria. Progression free survival is according to iwCLL definition.

Completed UC-961 Phase 1 Clinical Trial (UC-961 q 14 days x 4 doses)

Screen for eligibility for UC-961 Extension Trial

- √ Tolerated UC-961 without dose limiting toxicity and recovered from toxic effects to grade 1 or baseline.
- √ If intervening CLL therapy, maintains measurable disease.

UC-961 q 14 days x 4 doses, then q 28 days x 4 doses (dose based on ongoing phase 1 trial)

Response assessment (labs, imaging, bone marrow biopsy)

Repeat UC-961 course (dose increase if PD or SD)

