2.5 Secondary Endpoints

- **2.5.1** Overall response rate by IWCLL criteria following 6 months of biweekly dosing of UC-961 (Hallek *et al.*, 2008)
- **2.5.2** Progression free and overall survival (progression determined by IWCLL working group criteria)
- 2.5.3 SD, PR, and MRD- rates, as well as individual components of response (reduction in leukemia count, reduction in adenopathy and splenomegaly, and improvement in BM function), as determined by IWCLL working group criteria.

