4.10 Duration of Follow Up

Patients removed from study treatment for unacceptable adverse events will be followed until resolution or stabilization of the adverse event. Patients will be followed after removal from study treatment every 28 days (+/-7 days) for 8 visits, then every 56 days (+/- 7 days) until death, lost to follow-up, withdrawal of consent, or initiation of subsequent therapy for disease progression (see Section 5 for assessments).

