5.5 Long term follow-up

Every 28 days (+/- 7 days) for 8 visits then every 56 days (+/- 7 days), until discontinuation of trial participation:

- **5.5.1** Complete history and physical examination including vital signs (blood pressure, heart rate, temperature, weight) and organ measurements (i.e., lymph nodes, spleen, liver).
- **5.5.2** Adverse events grading and reporting.
- **5.5.3** Standard laboratory examinations: hematology (CBC w/differential), comprehensive metabolic panel (Na+, Cl-, K+, CO2, BUN, Creatinine, Glucose, Ca2+, total protein, albumin, total bilirubin, SGPT, SGOT, alkaline phosphatase), phosphorous, magnesium, uric acid, LDH.
- **5.5.4** Collection of correlative lab samples.

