- Platelets >100,000/µL or 50% improvement from pre-treatment value;
- Hemoglobin >11.0 g/dl (un-transfused) or 50% improvement from pre-treatment value.

Progressive Disease: Characterized by any one of the following events:

- ≥50% increase in the products of at least two lymph nodes on two consecutive determinations two weeks apart (at least one lymph node must be ≥2 cm); appearance of new palpable lymph nodes.
- ≥50% increase in the size of the liver and/or spleen as determined by measurement below the respective costal margin; appearance of palpable hepatomegaly or splenomegaly, which was not previously present.
- An increase in the number of blood lymphocytes by 50% or more with at least 5000 B lymphocytes per microliter.
- Transformation to a more aggressive histology (i.e., Richter's syndrome or prolymphocytic leukemia with ≥56% prolymphocytes).
- During therapy, patients not fulfilling the above criteria for progressive disease but demonstrating a decrease in hemoglobin >2 gm/dL, decrease >50% in platelet or granulocyte count will not be rated as progressive disease because these may occur as both a consequence of therapy. A bone marrow biopsy in such settings is strongly encouraged. Furthermore, during therapy, patients with progressive lymphocytosis but not any other findings of hemoglobin, platelet count, lymph node size, or spleen size meeting criteria for progressive disease will not be rated as progressive disease as agents that target the akt pathway have been demonstrated to induce a redistributive lymphocytosis as part of the mechanism of action (Byrd et al., 2013).
- After treatment, The progression of any cytopenia (unrelated to autoimmune cytopenia), as documented by a decrease of Hgb levels by more than 20 g/L (2 g/dL) or to less than 100 g/L (10 g/dL), or by a decrease of platelet counts by more than 50% or to less than 100 × 10⁹/L (100 000/µL), which occurs at least 3 months after treatment, defines disease progression, if the marrow biopsy demonstrates an infiltrate of clonal CLL cells.

Stable Disease: Patients who do not fulfill the criteria for complete or partial response as defined above but do not exhibit progressive disease will be considered as having stable disease.

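### Section 4.8 removes a patient given prohibited therapy from the study, while 4.10 and the synopsis keep such patients in follow-up; read literally, later AE and PFS/OS data are lost (minor)

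*Combined protocol and SAP*

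**What the plan says.** Section 4.8 prohibits concurrent anticancer therapy in patients receiving UC-961. It also prohibits corticosteroids above prednisone 20 mg daily (or equivalent) for more than 14 days, including for conditions other than CLL. The consequence is mandatory: "If these treatments are administered the patient will be removed from study". Removal from study is also the subject of 4.11.

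Section 4.10 takes the end of study treatment as its starting point: "Patients will be followed after removal from study treatment every 28 days (+/-7 days) for 8 visits", then every 56 days. That follow-up ends for death, loss to follow-up, withdrawal of consent, or new therapy for progression. The synopsis introduces the same four reasons with "Participation in the study and long-term follow-up will continue until one of the following". Prohibited therapy in a patient without progression is on neither list.

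Section 5.5 sets the follow-up visits, which run "until discontinuation of trial participation". Each includes AE grading, a CBC and "organ measurements (i.e., lymph nodes, spleen, liver)".

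Two sets of endpoints draw on these visits. The primary endpoint in 2.4.1 covers AEs during treatment and a 3-month follow-up. The secondary endpoint in 2.5.2 is "Progression free and overall survival (progression determined by IWCLL working group criteria)".

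**The concern.** A coordinator who applies 4.8 as written takes the patient off the study, and the 5.5 visits then stop. A coordinator who applies 4.10 stops the drug and keeps the visits. The two give different data for the same patient, and 4.8 does not say which is meant. Elsewhere the protocol has wording for stopping the drug alone: 4.6 does so for a DLT and 4.6.2 for repeated or severe infusion reactions.

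The trigger need not be progression. Section 4.6.1 expects patients with autoimmune cytopenia or pneumonitis to be held and then to resume. If such an event were treated with steroids beyond the 4.8 limit (an assumption, since the protocol does not specify treatment), the patient would be removed. The loss of follow-up could then be related to toxicity, in a study whose primary aim is safety.

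**Working it through.** The plan has no power calculation or other figure to reproduce here. The check compares the texts and then sizes the loss under stated assumptions.

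**1. When follow-up ends**

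| Section | Event | Does it cover prohibited therapy without progression? |
|---|---|---|
| 4.8 | Mandatory removal from study | Yes, this is the trigger |
| 4.10 | Four reasons for ending follow-up | No |
| Synopsis | The same four reasons | No |
| 4.11 | Investigator discretion, with an open list of reasons | Permitted, not required |
| 5.5 | Visits stop when participation stops | Follows whichever reading is used |

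If the prohibited therapy is given for progression, 4.10 already ends follow-up. The conflict is therefore limited to patients without progression.

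**2. Weight of one patient.** The synopsis anticipates 33 patients, with up to 75 eligible: 1/33 = 3.0% and 1/75 = 1.3%.

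**3. Safety window.** Assume that the 3-month follow-up is 91 days from the last dose; the documents do not state its start. Section 8.6.1 covers SAEs for 30 days after the last dose. The other 91 − 30 = 61 days depend on the 5.5 visits.

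**4. One hypothetical patient, literal reading.** Last dose on Day 85 and steroids above the limit from Day 90. The limit is passed on the 15th day of steroids, Day 90 + 14 = Day 104, when the patient is removed. Visits are counted from removal.

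- End of the safety window: 85 + 91 = Day 176.
- End of SAE reporting: 85 + 30 = Day 115.
- AE visits lost inside the window: 104 + 28 = Day 132 and 104 + 56 = Day 160. The next, 104 + 84 = Day 188, falls outside even at its earliest (Day 181).
- No scheduled collection of new non-serious AEs: 176 − 104 = 72 days.
- No reporting of new SAEs: 176 − 115 = 61 days.
- All eight 28-day examinations and CBCs are lost, from Day 132 to 104 + 8 × 28 = Day 328.

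**5. Progression.** Under 7.2, a post-treatment cytopenia with marrow confirmation counts only from a late time point: "which occurs at least 3 months after treatment, defines disease progression". In the example that is Day 176, which is 72 days after removal. More generally, the longest planned gap since the last dose within a course is the 28-day interval plus the 28-day maximum delay (4.6.1, note 2), or 56 days with visit windows ignored. That is 91 − 56 = 35 days short, so a patient removed during a course would not be seen when this criterion first applies. The node, spleen and liver measurements and CBCs at 5.5 visits are lost too, so the loss does not depend on imaging.

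**6. Effect on detecting a late AE.** Assume that 5%, 10% or 20% of patients are removed under 4.8 (rounded up), that they contribute nothing to late-AE data, and that the true late-AE rate is 5%. The chance of at least one case among n followed patients is 1 − 0.95ⁿ.

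| Planned N | None removed | 5% removed | 10% removed | 20% removed |
|---|---|---|---|---|
| 33 | 81.6% (n = 33) | 79.6% (n = 31) | 77.4% (n = 29) | 73.6% (n = 26) |
| 75 | 97.9% (n = 75) | 97.4% (n = 71) | 96.8% (n = 67) | 95.4% (n = 60) |

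Neither the removal share nor the AE rate is in the documents. The table shows only that the loss is small unless removals are common.

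**The case against.** The strongest reply is that the protocol, read as a whole, means drug only. A patient removed under 4.8 has also stopped study treatment, so 4.10 applies on its face and makes no exception for prohibited therapy. The synopsis lists "Adverse Events requiring removal from study" among the reasons for leaving protocol therapy, and 4.10 plainly still follows those patients, so the protocol does use the phrase loosely. This reading is plausible. It does not settle the matter, because 4.8 is mandatory and neither refers to 4.10 nor names treatment.

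Section 4.11 allows withdrawal at the investigator's discretion and its list of reasons is open. That is correct, but discretion does not explain a rule that leaves none.

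The toxicity case is the best protected. Section 8.1 follows an existing AE until it resolves, is otherwise explained or the patient dies; 4.10 follows patients removed for unacceptable AEs until resolution or stabilization; and 8.6.1 covers SAEs for 30 days after the last dose. This stands. What remains exposed is a new, different AE, together with PFS and OS.

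Stopping data collection after a confounding therapy could be a deliberate choice. If so, 4.10 and the synopsis should list it as a reason for ending follow-up. Confounded response or progression data can also be flagged at analysis, which needs the data to exist.

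Finally, no frequency is given, and the day counts come from one constructed patient. That is accepted and limits the severity.

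**Conclusion.** The concern holds as a minor point. Section 4.8 states a rule that, followed literally, conflicts with 4.10 and the synopsis and stops data that 2.4.1 and 2.5.2 call for in patients without progression. The effect rests on the literal reading and on an unknown number of patients, possibly none. The day counts also assume a 91-day window from the last dose.

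The main results are largely protected. All dosed patients remain evaluable for safety (7.1.1 and 10.0), AEs and withdrawals already counted do not change, the 28-day DLT rate is little affected, and section 10.0 plans no hypothesis test. A missing Day 169 or Day 365 response assessment is not part of this point: no text expressly requires one after any early discontinuation, which is a separate gap.

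**What to change.** In 4.8, change the consequence to removal from study treatment, with follow-up continuing under 4.10 and 5.5. State that AEs are collected through at least the 3-month follow-up. Follow-up then ends only for the four reasons in 4.10 and the synopsis, or on withdrawal under 4.11.

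Record the prohibited agent, its start date and the reason for it in the case report form, so that later response and progression data can be flagged. This has to be stated. Section 4.11 already requires the reason for discontinuation to be documented and the schedule in 6.0 includes medication review, but 5.2.2 keeps current medications out of the case report forms.

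The cost is one amended sentence, one case report form entry for each affected patient, and a few more visits on the existing schedule.

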The study proposed herein will allow patients who wish to continue UC-961 therapy to receive continued UC-961 at the biologically active dose or recommended phase 2 dose (RP2D). It will also allow patients that were initially treated at doses below the RP2D to increase their dose of UC-961. It will also allow for improved data regarding long-term safety and safety with prolonged dosing of UC-961 at the R2PD.

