4.2 Dose Limiting Toxicity

Dose-Limiting Toxicity (DLT) is defined as any of the following adverse events that are considered by the investigator to be possibly, probably, or definitely related to the study agent UC-961 within the 28 days of the start investigational treatment:

- CTCAE Grade 3 or higher non-hematologic toxicity, except for: Grade 3 infections lasting < 7 days that have resolved, or one occurrence of Grade 3 infusion reaction; or
- Grade 4 or higher hematologic toxicity (by modified iwCLL criteria); or
- Any AE requiring a dose delay of greater than 28 days;

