8.6 Reporting Requirements for Adverse Events

8.6.1 Expedited Reporting

- The Principal Investigator must be notified within 24 hours of learning of any serious adverse events, regardless of attribution, occurring during the study or within 30 days of the last administration of the study drug.
- The UCSD Human Research Protections Program (HRPP) must be notified within 10 business days of "any unanticipated problems involving risk to subjects or others" (UPR).

The following events meet the definition of UPR:

- 1. Any serious event (injuries, side effects, deaths or other problems), which in the opinion of the Principal Investigator was unanticipated, involved risk to subjects or others, and was possibly related to the research procedures.
- 2. Any serious accidental or unintentional change to the IRB-approved protocol that alters the level of risk.
- 3. Any deviation from the protocol taken without prior IRB review to eliminate apparent immediate hazard to a research subject.
- 4. Any new information (e.g., publication, safety monitoring report, updated sponsor safety report), interim result or other finding that indicates an unexpected change to the risk/benefit ratio for the research.
- 5. Any breach in confidentiality that may involve risk to the subject or others.
- 6. Any complaint of a subject that indicates an unanticipated risk or that cannot be resolved by the Principal Investigator.
- The FDA should be notified within 7 calendar days of any unexpected fatal or life-threatening adverse event with possible relationship to study drug, and 15 calendar days of any adverse event that is considered: 1) serious, 2) unexpected, and 3) at least possibly related to study participation.

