10.0 STATISTICAL CONSIDERATIONS

The primary aim of the study is to determine the safety of UC-961 therapy given at the currently used, biologically active dose, or RP2D for an extended duration.

Safety will be assessed through summaries of adverse events, clinical laboratory abnormalities, and changes in physical exam and vital signs. All subjects who receive a single dose of study medication will be considered evaluable for safety.

Adverse events will be listed, documenting the course, outcome, severity, and relationship to the study treatment. Incidence rates of AEs and the proportion of subjects prematurely withdrawn from the study due to AEs will be shown.

The primary endpoint of this study is the rate of dose-limiting toxicity (DLT).

SECONDARY ANALYSIS

Secondary Endpoints are overall response rate by IWCLL criteria following 6 months of biweekly dosing of UC-961 (Hallek *et al.*, 2008); Progression free and overall survival (progression determined by IWCLL working group criteria); and SD, PR, and MRD-rates, as well as individual components of response (reduction in leukemia count, reduction in adenopathy and splenomegaly, and improvement in BM function), as determined by IWCLL working group criteria.

These secondary endpoints will be summarized by dose cohort, clinical characteristics and overall using percentages, means and median survival estimates as appropriate. Data will also be presented graphically with Kaplan Meier plots, box plots, and bar charts. All statistics will be presented with 95% confidence intervals. The analysis will be descriptive; thus no correction for multiple analyses will be made and no formal tests of hypothesis will be done.

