11.4 Data and Safety Monitoring

In addition to adverse event monitoring and clinical oversight by the principal investigator and co-investigators, quality assurance of the study will be performed by the clinical trials office internal monitor.

This study will also use the UCSD Moores Cancer Center Data Safety and Monitoring Board (DSMB) to provide oversight in the event that this treatment approach leads to unforeseen toxicities. Data from this study will be reported after every 6 months, or sooner if required for clinical study stopping rules (Section 4.9), and will include:

- 1) the protocol title, IRB protocol number, and the activation date of the study.
- 2) the number of patients enrolled to date
- 3) the date of first and most recent patient enrollment
- 4) a summary of all adverse events regardless of grade and attribution
- 5) a response evaluation for evaluable patients when available
- a summary of any recent literature that may affect the ethics of the study.

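### The Section 4.9 enrolment hold does not count most types of dose-limiting toxicity, so a non-fatal cluster prompts no automatic early DSMB review: a narrow gap that is cheap to close

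*Combined protocol and SAP*

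**What the plan says.** Section 4.2 defines a DLT among events that the investigator considers at least possibly related and that occur within 28 days of starting treatment. It has three parts:

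- "CTCAE Grade 3 or higher non-hematologic toxicity", with two Grade 3 exceptions (a short, resolved infection and a single infusion reaction);
- "Grade 4 or higher hematologic toxicity (by modified iwCLL criteria");
- an adverse event that forces a dosing delay of more than 28 days.

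The study-level rule is at the end of Section 4.9. Enrolment is held until the DSMB has reviewed and approved, on either of two triggers: a death, or "2 or more non-hematologic Grade 4 events at least possibly attributable to the study drug".

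Section 11.4 sets the DSMB's timetable: "Data from this study will be reported after every 6 months, or sooner if required for clinical study stopping rules (Section 4.9"). The routine report includes "a summary of all adverse events regardless of grade and attribution".

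Section 10 states: "The primary endpoint of this study is the rate of dose-limiting toxicity (DLT"). Section 2.4.1 words the primary endpoint more broadly, as adverse events during treatment and three months of follow-up; a DLT is also an adverse event. Neither section gives an unacceptable rate or a monitoring bound.

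**The concern.** The event that Section 10 makes primary is not the event that the study-level rule counts. A run of related Grade 3 organ toxicities, or of Grade 4 cytopenias, would raise the DLT rate without reaching either trigger. Because early DSMB reporting depends on the same triggers, the protocol would not require the board to look before its next 6-monthly report.

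Prior exposure reassures only in part. Entrants tolerated UC-961 without a DLT in phase 1, but not always at the extension dose. Section 1.1 says of this study: "It will also allow patients that were initially treated at doses below the RP2D to increase their dose of UC-961". Sections 1.4 and 4.1 also let the extension dose rise as phase 1 advances. At stake is how many further patients start treatment before an independent group looks at a cluster.

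**Working it through.** The plan states no DLT threshold or stopping probability, so there is no figure to reproduce. Step 1 uses the text alone. In the later steps every rate is an assumption.

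**Step 1. Section 4.2 against Section 4.9.**

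| Non-fatal related DLT | Enrolment hold under 4.9 |
|---|---|
| Grade 3 non-hematologic | None at any count |
| Grade 4 hematologic | None at any count |
| Delay over 28 days | None, unless the event is also Grade 4 non-hematologic |
| Grade 4 non-hematologic | From the second event |

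In the other direction, neither 4.9 trigger has a 28-day limit and the death trigger has no attribution limit, so 4.9 also reaches events that are not DLTs.

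**Step 2. How often the Grade 4 trigger would stay silent.** Take n = 33 (the synopsis figure), DLT rate d, share f of DLTs that are Grade 4 non-hematologic, one DLT per patient and no deaths. P(silent) = P(Bin(33, d·f) ≤ 1).

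| d | f = 0 | f = 10% | f = 25% | f = 50% |
|---|---|---|---|---|
| 20% | 100% | 86% | 50% | 14% |
| 25% | 100% | 80% | 38% | 7% |
| 1/3 | 100% | 70% | 23% | 2% |

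The f = 0 column is true by construction. An independent death risk m per patient multiplies each entry by (1 − m)^33. At d = 25% and f = 10%, 0.801 becomes 0.411 (m = 2%) or 0.147 (m = 5%). Grade 4 events after day 28 lower it further. The gap therefore matters mainly when DLTs are Grade 3 non-hematologic or Grade 4 hematologic and deaths are few.

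**Step 3. What an added count would do.** Illustrative bound: the smallest x with P(rate > p0 | x DLTs in n) > 0.90 under a Beta(0.5, 0.5) prior, that is, 1 − BetaCDF(p0; 0.5 + x, 0.5 + n − x) > 0.90, from the third patient on. The cells give the largest n at which x DLTs reach the bound.

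| DLTs x | p0 = 20% | 25% | 30% |
|---|---|---|---|
| 2 | 4 | 3 | 3 |
| 3 | 7 | 6 | 5 |
| 4 | 11 | 9 | 7 |
| 5 | 14 | 12 | 10 |
| 6 | 18 | 15 | 12 |
| 7 | 22 | 18 | 15 |
| 8 | 26 | 21 | 18 |
| 9 | 30 | 24 | 20 |
| 10 | 34 | 28 | 23 |
| 11 | – | 31 | 26 |
| 12 | – | 34 | 29 |
| 13 | – | – | 32 |
| 14 | – | – | 34 |

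Exact sequential probability of a hold by patient 33, with outcomes known in order:

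| True DLT rate | 5% | 10% | 20% | 25% | 1/3 |
|---|---|---|---|---|---|
| p0 = 20% | 1.6% | 7% | 36% | 57% | 85% |
| p0 = 25% | 0.9% | 4% | 22% | 38% | 70% |
| p0 = 30% | 0.8% | 3% | 15% | 25% | 52% |
| p0 = 25%, looks at 6, 12, 18, 24, 30, 33 only | 0.2% | 2% | 16% | 31% | 64% |

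With 75 patients and p0 = 25%, the figures are 0.9%, 4%, 23%, 44% and 85%.

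**Step 4. The counting basis matters.** Suppose a patient with a DLT is counted at once, but a patient without one only after 28 days. The early DLT fraction is then biased upward. Simulation with the 25% bounds, 33 patients enrolled evenly and a true 10% rate gives unneeded holds of about 8% (12-month accrual) or 13% (6-month accrual) if all DLTs fall on day 1. If they are spread evenly over 28 days, it gives about 6% or 8%. The unbiased figure is 4%.

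**Step 5. Exposure until the next report.** If 33 patients enrol evenly over 1, 2 or 3 years, the number starting in six months is 33/12 × 6 = 16.5, 33/24 × 6 = 8.25 or 33/36 × 6 = 5.5. These are worst cases. If the cluster falls at a random time between reports, the average is half of each.

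**The case against.** **Dose clearance.** Sections 1.4 and 4.1 limit dosing to levels found safe in the parent trial, which uses a 3+3 design (Section 1.1). That trial gave four doses 14 days apart, so it covers the 28-day DLT window. This stands as a real count-based control. It rests on small cohorts, however: at a true 25% rate, three patients show no DLT with probability 0.75³ = 42%.

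**Individual protection and reporting.** A DLT ends that patient's treatment (4.6), and 4.5 bars dosing during ongoing severe related toxicity. Under 8.6.1 serious events reach the principal investigator in 24 hours. Unexpected related events go to the FDA in 7 days if fatal or life-threatening, or 15 days if serious. Unanticipated problems go to the HRPP in 10 business days, including an "interim result or other finding that indicates an unexpected change to the risk/benefit ratio for the research". Section 9.1 lists no identified toxicities, so many serious DLTs would count as unexpected. This also stands. But none of these routes is a numerical hold or names the DSMB, and a non-serious laboratory DLT may bypass them.

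**Hematologic events.** Section 7.1.2 explains that many CLL patients start with low counts, so leaving Grade 4 cytopenias out of an automatic hold is defensible. That reason does not extend to Grade 3 non-hematologic DLTs.

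**Likely rate.** Entrants are selected as free of DLT, and the tabulated phase 1 events are Grade 1 or 2. Rates of 20% to one-third may be far too high. This is the main reason to keep the severity modest.

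A reader might infer that a DLT cluster would go unseen, or that action would rest on the investigator alone until the next DSMB report. The expedited routes and the 6-monthly summary of all adverse events do not support that.

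**Conclusion.** The gap holds, in a narrow form. Sections 4.2, 4.9 and 11.4 together leave non-fatal Grade 3 non-hematologic, Grade 4 hematologic and delay-based DLTs without any count that holds enrolment or brings the DSMB in early. This follows from the text and needs no assumed rate.

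Its size does depend on assumptions: the DLT rate, the Grade 4 non-hematologic share, the death risk and the speed of accrual. None of these is in the documents. With a DLT rate of 5% to 10%, which prior tolerance makes plausible, there would rarely be a cluster to catch. The documents do not support a stronger reading, namely that patients are unprotected or that the analysis is invalid: no statement in the plan is wrong, and the descriptive analysis is unaffected. Low to moderate severity; a cheap improvement.

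**What to change.** Keep both triggers in 4.9 and add a third: enrolment is held, with unscheduled DSMB review, when the cumulative number of patients with a Section 4.2 DLT reaches a bound set by the number treated. Three details need stating.

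1. **Limit.** The sponsor's clinicians and the DSMB choose the unacceptable rate. The tables above are illustrations. A 20% limit is more sensitive than 25% but causes more unneeded reviews.
2. **Timing and denominator.** Check at each DLT. Bring patients with and without a DLT into the count on the same basis: either in order of enrolment once each 28-day outcome is known, or with partial follow-up weighting. In-order counting can lag by up to 28 days, during which about 33 × 28/365 = 2.5 patients start under one-year accrual.
3. **Delay-based DLTs.** Add these when established, even after day 28. The first infusion that can be delayed is due on day 15, so a delay of more than 28 days cannot be complete before day 15 + 28 = 43.

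Related events after the DLT window stay under the existing triggers and the 6-monthly report, unless the sponsor chooses to count them.

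The cost is one bullet and a short table. No new data are needed, because DLTs are already identified under 4.2 and 4.6. The downside is an occasional unneeded review: with the 25% illustration, about 4% at a true 10% DLT rate and 1% at 5%, for 33 or 75 patients. If the counting basis is left uneven, the 4% rises to roughly 6–13% with accrual over 6 to 12 months.
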